4. RMT*
5. TMS and gambling-cues exposure
6. HR/PB monitoring
7. VAS craving
8. Side effects questionnaire and PANAS
9. Interval \geq 60 minuti
10. Steps 6,7 and 8 will be repeated

Participants will receive 20 sessions of rTMS during the continued rTMS treatment phase (2 sessions daily, 5 days/week), and subsequently will undergo 24 sessions during the follow-up (FU) phase (two consecutive sessions per day for 12 weeks), for a total of 44 sessions over the course of the study.

During each stimulation session and immediately after, hearth rate and blood pressure will be monitored. Also, at the end of the session, the ‘Side Effect’ questionnaire and the PANAS scale will be administered to evaluate potential side effects.

Side effects: The use of rTMS is considered safe when conducted within existing safety guidelines (Rossi et al. 2009). On the basis of these guidelines, it has been developed a screening tool, named the TMS safety screening, which will be administered to all study participants to determine their eligibility. Several side effects have been reported following TMS. The most important risk of rTMS is the possibility of inducing a seizure. The 1996 and 2008 International Consensus Safety Guidelines describe the maximum safe duration of an rTMS train based on intensity and frequency of the stimulation. Since the issuance of these guidelines, the incidence of TMS-induced seizures worldwide is very low, estimated as “rare” with low-frequency (< 1 Hz) rTMS and < 1% with high-frequency (> 1 Hz) rTMS. There have been no reports of any subject developing epilepsy or repeated spontaneous seizures after rTMS. All rTMS-induced seizures to date have been transient and self-limiting, without long-term sequelae.

Concurrent medication has been implicated as a risk factor in some of the seizures reported with rTMS. Some have suggested that certain medications, e.g. tricyclic antidepressants and neuroleptics, should be contraindicated in those receiving rTMS. To minimize risk, psychotropic medications will be exclusionary criteria in the current study, and use of illicit drugs will be monitored. Although data are lacking, a history of epilepsy, of seizures of other origin (other than febrile child fevers) could also be associated with an increase of TMS-induced seizures, and will therefore also be exclusionary criteria. To manage the small risk nevertheless present, a physician will be available while TMS sessions are in progress and will be called in the event of any medical issue.

Mild headache responding readily to non-opioid analgesics has been reported as on the most common side-effect of rTMS reported in depression treatment trials. It may result from direct stimulation of superficial facial muscles or nerves, as rTMS may cause an uncomfortable facial twitch. Headaches usually go away promptly with nonprescription medication, such as acetaminophen, which will be offered to subjects as needed.

Hearing Impairment: Rapid excitation of the stimulation coil produces clicks that have resulted in transient increase in the auditory threshold of human subjects. This should not occur if earplugs are used. If a subject reports or if an investigator observes that a subject’s earplug has loosened or fallen out, investigators will immediately stop applying.

rTMS-Induced Manic Effects: Mania has been induced in a small number of healthy and depressed subjects by high-frequency rTMS to the left dorsolateral prefrontal cortex.

In all the above cases, the psychiatric side-effects induced by rTMS were transient, resolving with the cessation of rTMS or rapidly responding to pharmacological treatment.

Although not limited to, the risk for psychiatric complications appears to be existing predominantly in subjects with pre-existing psychiatric morbidity. An important means of minimizing risk in the current proposed study is therefore to exclude this population. Furthermore, mood symptoms will be monitored using a validated rating scale, and will provide an additional indication of hypomanic or manic symptoms (YMRS, PANAS, CPRS).

Questionnaires and Rating Scales

- TMS Safety Screen: A questionnaire that aids in determining appropriateness of administering TBS. Completion time: < 5 minutes.
- Visual Analogue Scale for Craving (VAS-craving): VAS is a horizontal line, 100 mm in length, anchored by word descriptors at each end (0 = lower scores; 10 = higher scores). The patient marks on the line the point that they feel represents their perception of their current state. Completion time: < 5 minutes.
- Pathological Gambling Adaptation of the Yale-Brown Obsessive-Compulsive Scale (PG-YBOCS): A 10-item clinician-administered questionnaire that measures the severity of PG over the past one week. Completion time: < 5 minutes.
- Gambling Symptom Assessment Scale (G-SAS): A 12-item self-rated scale designed to assess gambling symptom severity and change during treatment. Completion time: < 5 minutes.

As time permits during the screening visit and after consenting, baseline characterization measures will also be collected. Participants may be scheduled for an additional visit and the necessary additional time to complete these assessments prior to beginning the 10-day rTMS treatment session. Following this, subjects will have 8 follow-up visits [at the end of continued rTMS treatment phase, at rTMS follow-up visit #2, #4, #8, #12, and once a month during no rTMS follow-up phase].

Characterization measures include:

- Hamilton Anxiety Scale (HAM-A): A 21-item self-report inventory, which assesses the severity of anxiety. Completion time: ~ 5 minutes.
- Montgomery-Asberg Depression Rating Scale (MADRS): A clinical assessment to identify symptoms of depression. This assessment is especially useful in identifying changes in depression symptoms over time. Completion time: < 10 minutes.

- Positive and Negative Affect Scale (PANAS): A self-report scale to assess state-level affect. Completion time: < 5 Minutes.
- Profile of Mood States (POMS): A questionnaire designed to measure present mood state by a list of adjectives on a 5-point Likert scale and measures six dimensions of affect, including tension-anxiety, depression-dejection, anger-hostility, vigor-activity, fatigue-inertia, and confusion-bewilderment. The measure has been shown to produce reliable and valid profiles of mood state. Completion time: ~ 5 minutes.
- Snaith-Hamilton Pleasure Scale (SHAPS): A 14-item self-report scale designed to measure hedonic-tone/anhedonia. Completion time: ~ 5 minutes.
- Temporal Experience of pleasure Scale (TEPS): A 20-item self-report scale designed to evaluate individual trait dispositions in anticipatory and consummatory pleasure experiences. Completion time: ~ 15 minutes.
- Time-line follow back (TLFB). The TLFB will be used to assess substance use behavior. This assessment will be either self-administered or administered by one of the investigators. Participants will read the instructions and/or will be guided by the therapist or investigator in filling out the calendar. A lifetime TLFB will be administered at baseline and during each visit.

Cognitive Function will be assessed at baseline, at the end of continued rTMS treatment phase, at the end of rTMS follow-up phase and at the end of the no rTMS follow-up phase. Cognitive Assessment include:

- Iowa Gambling Task: to assess decision-making process. Completion time: ~ 15 min.

E. Study Design

The study itself will consist of three phases.

(1) an outpatient screening phase, during which patients will be screened to assess their eligibility to be enrolled in the study. This phase will include informed consent and randomization, and will conclude with baseline data collection.

(2) a continued rTMS treatment phase, during which subjects will receive 20 stimulation sessions (2 daily, 5 days/week). In addition to this, participants will also attend self-help groups twice per week, as part of standard-of-treatment for GD.

During this phase, treatment response will be assessed by evaluating the long-term effect of treatment on relapse rate, gambling severity and craving, mood and cognition.

(3) a follow-up phase of 24 weeks, which will be structured as following. During the first 12 weeks (rTMS follow-up) subjects will be asked to return to the Outpatient Clinic for an outpatient visit. During these visits, participants will undergo real stimulation (two consecutive sessions per day), and will also attend self-help groups once per week.

During the following 12 weeks (no rTMS follow-up), participants will not receive TMS but behavioral and other data will be collected to observe long-term effects of rTMS.

If subjects are unable or unwilling to attend these visits, they will be contacted by phone or email, and an attempt will be made to obtain measures in this manner.

F. Objectives

Primary: The primary goal of the current study is to investigate the effects of repetitive transcranial magnetic stimulation (rTMS) targeting the left DLPFC on gambling craving. The co-primary goal is to investigate rTMS effect on gambling behavior.

Secondary: Our secondary goals are to evaluate rTMS effects on: (1) mood; (2) cognitive functions.

Outcomes measures: Our primary outcomes will be: (1) change in gambling craving score as measured by the Visual Analogue Scale for Craving (VAS-craving) from pre- to post treatment [baseline and after rTMS treatment: 2 weeks, 3 months, 6 months]; (2) changes in gambling behavior as measured by TLFB self-reports, Pathological Gambling Adaptation of the Yale-Brown Obsessive-Compulsive Scale (PG-YBOCS), Gambling Symptom Assessment Scale (G-SAS) [baseline and after rTMS treatment: 2 weeks, 3 months, 6 months]. Our secondary outcomes are: (1) Changes in the scores on the the Montgomery-Asberg Depression Scale (MADRS) from pre- to post treatment [baseline and after rTMS treatment: 2 weeks, 3 months, 6 months]; (2) changes in the scores on the Hamilton Anxiety Rating Scale (HAM-A); (3) changes in the scores of the Iowa Gambling Task from pre- to post treatment [baseline and after rTMS treatment: 2 weeks, 3 months, 6 months]; (4) changes in the scores of the anhedonic symptoms assessed by Snaith Hamilton Pleasure Scale (SHAPS) and Temporal experience of Pleasure Scale (TEPS) from pre- to post treatment [baseline and after rTMS treatment: 2 weeks, 3 months, 6 months]; (5) changes in the scores of the anhedonic symptoms assessed by changes in Profile of Mood States (POMS) from pre- to post treatment [baseline and after rTMS treatment: 2 weeks, 3 months, 6 months].

1. Aims

Primary aim:

To determine the effects of rTMS on gambling craving and behavior in patients with GD.

- Changes in the Visual Analogue Scale for Craving (VAS-craving) from pre- to post treatment [baseline and after rTMS treatment: 2 weeks, 3 months, 6 months];
- Changes in the Pathological Gambling Adaptation of the Yale-Brown Obsessive-Compulsive Scale (PG-YBOCS) from pre- to post treatment [baseline and after rTMS treatment: 2 weeks, 3 months, 6 months].
- Changes in Gambling Disorder Severity as assessed by Timeline Follow Back (TLFB) from pre- to post treatment [baseline and after rTMS treatment: 2 weeks, 3 months, 6 months].
- Change in Gambling Behavior as assessed by Gambling Symptom Assessment Scale (G-SAS) from pre- to post treatment [baseline and after rTMS treatment: 2 weeks, 3 months, 6 months].

Secondary aims:

- Changes in the Iowa Gambling Task (IGT) Performance from pre- to post treatment [baseline and after rTMS treatment: 2 weeks, 3 months, 6 months];
- Changes in the scores of the Montgomery-Asberg Depression Scale (MADRS) from pre- to post treatment [baseline and after rTMS treatment: 2 weeks, 3 months, 6 months];
- Changes in the scores on the Hamilton Anxiety Rating Scale (HAM-A) from pre- to post treatment [baseline and after rTMS treatment: 2 weeks, 3 months, 6 months];
- Changes in the scores on the Snaith Hamilton Pleasure Scale (SHAPS) and on the Temporal experience of Pleasure Scale (TEPS) from pre- to post treatment [baseline and after rTMS treatment: 2 weeks, 3 months, 6 months];
- Changes in the scores of the Profile of Mood States (POMS), from pre- to post treatment [baseline and after rTMS treatment: 2 weeks, 3 months, 6 months];

Statistical Analysis

Behavioral measures on each of the cognitive tasks as well as questionnaire data from each of the experimental conditions will be compared within the experimental group using

mixed, repeated-measures ANOVA, and linear mixed models. When assessing the statistical results from the behavioral and questionnaire data, a standard α -level of 0.05 will be used. Alpha-levels for multiple comparison follow-up tests will be corrected using an appropriate method (e.g., Bonferroni, Tukey, Scheffe).

G. Data Management and Safety measures

Safety: Participants will be presented with information about the study prior to data collection and they will be informed of their right to withdraw their information at any time, and that by taking part they are providing consent for the research team to use their anonymised data for research (including publications and other forms of dissemination) (informed consent and information sheets are attached as annexes, Italian version). Furthermore, they will provide written informed consent prior to the experiment, in line with the Helsinki Declaration developed by the World Medical Association. The research team will not include people if they are unable to give informed consent. The Health and Human Sciences Ethics Committee at the University of Chieti approved the research before it commences.

Randomization: We aimed to recruit a total of 10 patients for this open-label study. If data will suggest a potential role of rTMS in Gambling Disorder, we will proceed to a randomized placebo-controlled trial to verify our hypothesis.

Data collection and storage: Collected personal data will be identified via specific individual codes. Datasets will be anonymized by removing all direct identifiers, (e.g., name, address, telephone numbers), but also indirect identifiers and other information that could lead to "deductive disclosure" of participants' identities. The computer files will be password protected, and only accessed by agreed members of the team. Files will be shared to other involved institutions via secure server. Hard copies such as interview notes, questionnaires and psychometric scales will be kept securely locked in a cabinet that will only be accessed by agreed members of the research team. As a part of the informed consent, participants will be informed on what will happen to the data they will provide, and specifically: a) on how the data will be stored; b) on who will access the data; c) on how long the data will be kept for.

References

1. Volkow, N. D., Fowler, J. S., Wang, G. J., & Swanson, J. M. (2004). Dopamine in drug abuse and addiction: results from imaging studies and treatment implications. *Molecular psychiatry*, 9(6), 557-569.
2. Matochik, J. A., London, E. D., Eldreth, D. A., Cadet, J. L., & Bolla, K. I. (2003). Frontal cortical tissue composition in abstinent cocaine abusers: a magnetic resonance imaging study. *Neuroimage*, 19(3), 1095-1102.
3. Goldstein, R. Z., & Volkow, N. D. (2011). Dysfunction of the prefrontal cortex in addiction: neuroimaging findings and clinical implications. *Nature Reviews Neuroscience*, 12(11), 652-669.
4. Volkow, N. D., Fowler, J. S., & Wang, G. J. (2003). The addicted human brain: insights from imaging studies. *The Journal of clinical investigation*, 111(10), 1444-1451.
6. Jasinska, A. J., Chen, B. T., Bonci, A., & Stein, E. A. (2015). Dorsal medial prefrontal cortex (MPFC) circuitry in rodent models of cocaine use: implications for drug addiction therapies. *Addiction biology*, 20(2), 215-226.

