Design: After eligibility screening and informed consent, participants will undergo a baseline phase during which they will be randomized to receive high-frequency (15Hz) rTMS (active rTMS) stimulation of the left DLPFC. Subsequently, the continued treatment phase will take place, during which rTMS sessions will be conducted twice per day, five times per week for 2 weeks, for a total of 20 sessions. During this phase, participants will also undergo self-help groups twice a week. After this phase, participants will start a 24-week outpatient phase. (2) During the first 12 weeks (rTMS follow-up) participants will undergo real stimulation (two consecutive sessions weekly), and behavioral assessments will be performed.

During the following 12 weeks (no rTMS follow-up), participants will not receive TMS but behavioral data will be collected to observe long-term effects of rTMS. Visits will take place every two weeks, during this phase. During the follow-up period, patients will continue to participate in self-help groups.

Outcomes measures: Our primary outcomes will be: (1) change in craving score as measured by the Visual Analogue Scale for Craving (VAS-craving) from pre- to post treatment [baseline and after rTMS treatment: 2 weeks, 3 months, 6 months]; (2) changes in gambling behavior as measured by TLFB self-reports, Pathological Gambling Adaptation of the Yale-Brown Obsessive-Compulsive Scale (PG-YBOCS), Gambling Symptom Assessment Scale

(G-SAS) [baseline and after rTMS treatment: 2 weeks, 3 months, 6 months]. Our secondary outcomes are: Changes in the scores on the the Montgomery-Asberg Depression Scale (MADRS) from pre- to post treatment [baseline and after rTMS treatment: 2 weeks, 3 months, 6 months]; (2) changes in the scores on the Hamilton Anxiety Rating Scale (HAM-A); (3) changes in the scores of the Iowa Gambling Task from pre- to post treatment [baseline and after rTMS treatment: 2 weeks, 3 months, 6 months]; (4) changes in the scores of the anhedonic symptoms assessed by Snaith Hamilton Pleasure Scale (SHAPS) and Temporal experience of Pleasure Scale (TEPS) from pre- to post treatment [baseline and after rTMS treatment: 2 weeks, 3 months, 6 months]; (5) changes in the scores of the anhedonic symptoms assessed by changes in Profile of Mood States (POMS) from pre- to post treatment [baseline and after rTMS treatment: 2 weeks, 3 months, 6 months].

B. Background

Gambling disorders

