directed posteriorly. While supra-threshold stimuli will be applied, the coil will be moved in steps of 1 cm to determine the optimal scalp position for producing motor evoked potentials (MEP) of maximal amplitude (lowest threshold) in the contralateral target hand muscle. This procedure will be performed in order to identify the resting motor threshold (RMT), which will be used to calculate the intensity of stimulation (100% of the RMT). Subsequently, the coil will be placed over the left dorsolateral prefrontal cortex using a TMS Navigator. The motor hotspot and the DLPFC location will be marked on the cap wore by the participant so to ensure accuracy and consistency across sessions. Two consecutive rTMS sessions lasting 13 minutes each will be performed, with a minimum of 60 minutes interval between sessions. Each rTMS session will be delivered at the intensity of 100% of individual resting motor threshold, for a total of 40 trains (60 stimuli per train, inter-train interval of 15 seconds, for a total of 2400 stimuli). At the beginning of each session, participants will be exposed to gambling-related cues for approx. 2 minutes. While viewing pictures (approx. 60 images), participants will be instructed to try to inhibit any craving elicited by the cues in an attempt to elicit activation in networks specifically related to controlling responses and gambling behavior in general. At the end of each stimulation session, participants will rate their craving using a Visual Analogue Scale (VAS).

Study days during which participants will receive stimulation will be planned as follow:

1. Arrival
2. Tox drug screen
3. Preparation (earplugs, cap)

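### Does step 10 of the stimulation-day list, which repeats only steps 6 to 8, leave the number of rTMS sessions in doubt?

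*Combined protocol and SAP*

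**What the plan says.** Section D, under rTMS, describes a stimulation day twice: in prose and then as a numbered list.

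The prose before the list says "Two consecutive rTMS sessions lasting 13 minutes each will be performed, with a minimum of 60 minutes interval between sessions". It adds "At the beginning of each session, participants will be exposed to gambling-related cues" and "At the end of each stimulation session, participants will rate their craving using a Visual Analogue Scale".

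In the list, step 5 is "TMS and gambling-cues exposure". Step 6 is heart rate and blood pressure, step 7 the craving VAS, step 8 the side-effects questionnaire with PANAS, and step 9 an interval of at least 60 minutes. Step 10 reads "Steps 6,7 and 8 will be repeated".

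The prose after the list gives 20 sessions in the treatment phase and 24 in follow-up, "for a total of 44 sessions over the course of the study". It also says "During each stimulation session and immediately after, hearth rate and blood pressure will be monitored".

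The Précis (Design) and Section E also give two sessions per stimulation day in the treatment phase. For the first 12 weeks of follow-up, the Précis gives two consecutive sessions weekly and Section E gives two consecutive sessions per day.

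On visits in the later 12 weeks without stimulation, the Précis says "Visits will take place every two weeks, during this phase". Section D (Questionnaires and Rating Scales) counts eight follow-up visits: one at the end of treatment, four named rTMS follow-up visits, and monthly visits in the phase without stimulation. It also has the TLFB completed at baseline and at each visit.

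**The concern.** The list is the step-by-step instruction for every stimulation day, and step 5 is its only stimulation and cue step. Because step 10 does not name step 5, staff who worked only from the list would wait an hour and then repeat the monitoring, the craving rating and the questionnaires with no second stimulation or cue exposure before them. Half of the stated sessions would be lost. The second VAS of the day would also no longer be a rating made at the end of a stimulation session, which is how the prose defines it. In a single-arm study of 10 patients with craving as a primary outcome, doubt about how much stimulation was given would affect how any pre-to-post change is read.

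A second, separate doubt concerns the phase without stimulation. Two-weekly visits and monthly visits give different counts, and the TLFB, a primary-outcome instrument, is tied to each visit.

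**Working it through.** **Inputs**

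- Treatment phase: two sessions per day, 5 days per week, 2 weeks (Précis, Design; Section D repeats the daily and weekly frequency).
- First follow-up phase: 24 sessions, two per stimulation day, over 12 weeks (Section D); two sessions weekly (Précis).
- Stimuli per session: 40 trains of 60 (Section D).

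**Reproducing the stated total**

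- Treatment days: 2 × 5 = 10. Sessions: 2 × 10 = 20, as stated.
- Follow-up days: 24 / 2 = 12, one per week, which agrees with the Précis. Sessions: 2 × 12 = 24, as stated.
- Total: 20 + 24 = 44 over 10 + 12 = 22 days, as stated.

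Section D gives two sessions per day for 12 weeks without giving days per week. Five days per week would make 2 × 5 × 12 = 120 follow-up sessions, which its own 24 rules out. One day per week is the reading that fits.

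**The list followed to the letter**

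- Step 5 once per day: 10 + 12 = 22 stimulations, against 44.
- Stimuli per session: 40 × 60 = 2,400. Over the study, 22 × 2,400 = 52,800, against 44 × 2,400 = 105,600.
- VAS ratings: step 7 twice per day, 2 × 22 = 44.

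The last count is informative. The prose ties one VAS to the end of each stimulation session. Forty-four ratings therefore correspond to 44 sessions, and 22 stimulations would leave 22 ratings with no session to follow.

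**Step 10 beside the rest of the text**

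| Place | What it implies per stimulation day |
|---|---|
| Précis, Design | two sessions |
| Section D, prose before the list | two sessions, cues at the start of each |
| List, step 9 | the same 60-minute minimum that the prose places between sessions |
| List, steps 6 and 7 repeated | a second session, since monitoring and the VAS belong to each session |
| Section D, prose after the list | two sessions, 44 in all |
| Section E | two sessions |
| List, step 10 | does not name step 5 |

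One cross-reference stands against every other statement, including others within the same list.

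**Visits in the phase without stimulation**

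- Précis: 12 / 2 = 6 visits.
- Section D: 1 + 4 + 3 = 8, so 3 in this phase, taking monthly over 12 weeks as three.
- The same Section D sentence names only 4 of the 12 weekly stimulation visits. It therefore reads as a list of assessment visits, not of every attendance, and three monthly assessments can fall within six two-weekly visits.
- The TLFB would then be completed 3 or 6 times in this phase, depending on which visits are meant. Section F fixes the TLFB outcome at baseline, 2 weeks, 3 months and 6 months, so neither count changes the outcome.

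**The case for a change.** The strongest contrary case is that an instruction list should be correct as it stands. Staff may work from the list and not the paragraphs, the printed omission is complete and unambiguous, and the correction would take one line. That the intent can be inferred lowers the severity but does not make the text right. All of this is fair, and the list and the prose do need to be reconciled.

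What does not follow is a change to the trial's plan. The number of sessions is stated outright, in total and by phase, directly after the list. A reader who followed step 10 literally would have to disregard the paragraphs on both sides of it and would have an hour's interval with no purpose. The Statistical Analysis text uses neither the number of sessions nor the individual session ratings as a defined quantity, so no analysis changes with the wording.

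For the visit intervals, it can be said that the documents never state the nesting, and that the content of the extra two-weekly visits is unspecific. That is also true. But the Précis and Section E both say that behavioral data are collected in this phase, and Section D describes the TLFB as a lifetime calendar, so fewer administrations need not leave days uncovered. What remains is missing detail that study staff can settle in the visit schedule.

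**Conclusion.** The concern is factually correct and has no consequence for the plan. Step 10 omits step 5, and 22 against 44 is the right arithmetic for a literal reading. That reading is contradicted by the Précis, by the prose before and after the list, by Section E, and by the list's own interval and repeated ratings. The protocol's total of 44 is reproduced exactly from its stated frequencies. This is a clerical slip: reconciling the wording leaves the session totals, the outcome time points, the sample size of 10 and the analysis as they are. The wording is for the investigators to settle, and nothing here judges which stimulation schedule is clinically appropriate.

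The visit-interval question is a gap with a sensible reading. It amounts to 3 or 6 TLFB administrations in the last 12 weeks, and the outcome time points are fixed either way.

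The conclusion rests on two assumptions: one stimulation day per week in the first follow-up phase, the only frequency that gives 24 sessions at two per day over 12 weeks; and three monthly visits in the final 12 weeks, which is what makes the stated eight add up.

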
On the basis of these findings, the aim of this study is to test whether rTMS of the left DLPFC could be effective in treating GD.

C. Study Overview

This is an open-label study with a single arm: 15 Hz rTMS stimulation on the DLPFC. Participants will be 10 treatment-seeking patients, between the ages of 18-65, who meet diagnostic criteria for GD. Criteria for study enrollment are listed below. All participants will be informed about study procedures and will provide written informed consent prior to the experiment, in line with the Helsinki Declaration developed by the World Medical Association.

Recruitment: We aimed to recruit patients from rural and urban areas, in order to take account of possible differences in substance consumption and addiction severity. Therefore, recruitment will take place in two different cities: Rome, a large metropolitan area, and Chieti, a small city in the center of Italy, where the majority of patients will be enrolled from rural surroundings. Participants enrollment will be performed by a multidisciplinary team (physicians, psychologists), who have been trained and have extensive experience in performing the assessments included in the current study.

Inclusion criteria

1. Age 18 – 65;
2. Current diagnosis of Gambling Disorder, based on the Diagnostic and Statistical Manual of Mental Disorder – Fifth Edition (DSM-5);
3. Drug-free.

Exclusion criteria

1. Current DSM-5 diagnosis of substance use disorders other than nicotine
2. Current DSM-V diagnosis of moderate to severe alcohol use disorders
3. Current DSM-5 diagnosis of schizophrenia, bipolar disorder, or other psychotic disorder;
4. Use in the past 4 weeks of any medication with known proconvulsant action; or current regular use of any psychotropic medications (benzodiazepines, antipsychotic medications, tricyclic antidepressants, anti-epileptics, mood stabilizers);

5. Any history of any clinically significant neurological disorder, including organic brain disease, epilepsy, stroke, brain lesions, multiple sclerosis, previous neurosurgery, or personal history of head trauma that resulted in loss of consciousness for > 5 minutes and retrograde amnesia for > 30 minutes;
6. Any personal or family history (1st degree relatives) of seizures other than febrile childhood seizures;

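### The only description of the TLFB says it records substance use over a lifetime, yet the TLFB is a primary measure of change in gambling behaviour; the sections must be reconciled, with a named variable and comparison windows.

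*Combined protocol and SAP*

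**What the plan says.** **What the instrument is said to measure.** The TLFB entry in section D (Questionnaires and Rating Scales) states: "The TLFB will be used to assess substance use behavior". It describes a calendar, completed by the participant alone or with guidance, and adds: "A lifetime TLFB will be administered at baseline and during each visit". It does not mention gambling.

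**What the instrument is used for.** The outcomes paragraph of section F, in words repeated in the Précis, lists under the second primary outcome "changes in gambling behavior as measured by TLFB self-reports", together with the PG-YBOCS and G-SAS. The primary aim in section F (1. Aims) has "Changes in Gambling Disorder Severity as assessed by Timeline Follow Back (TLFB) from pre- to post treatment". The time points are baseline, 2 weeks, 3 months and 6 months.

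**Related text.** Section E (Study Design) says treatment response will be judged by "evaluating the long-term effect of treatment on relapse rate, gambling severity and craving, mood and cognition". The Statistical Analysis paragraph says "Behavioral measures on each of the cognitive tasks as well as questionnaire data from each of the experimental conditions will be compared" and names neither the TLFB nor a summary derived from it. The exclusion criteria in section C include "Current DSM-5 diagnosis of substance use disorders other than nicotine".

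**The concern.** The operational description of a primary measure names a different construct from the outcome it is meant to supply. Site staff who work from section D would ask about substance use. An analyst who works from section F would expect gambling data.

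The look-back is a second difficulty, and it remains if the construct is corrected. A change from baseline needs a defined period before treatment and defined periods afterwards. A lifetime calendar taken again at each visit contains the whole baseline period every time, and no section says which part of it is compared.

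The TLFB component of the co-primary gambling-behaviour goal is at stake. Of the three measures listed for that goal, the other two are described as severity or symptom scales, and only the TLFB is described as a calendar. If the variable and period stay open, they could be chosen after the data are seen. Section G makes the decision to proceed to a randomised placebo-controlled trial depend on what these data suggest.

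**Working it through.** The plan gives no figure on this point to reproduce. The check is a comparison of text with some counting.

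**1. Statements of the TLFB's purpose**

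| Place | Construct |
|---|---|
| Précis, Outcomes measures | Gambling behaviour |
| Section F, Outcomes measures | Gambling behaviour |
| Section F, 1. Aims | Gambling disorder severity |
| Section D, TLFB entry | Substance use |

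Three statements say gambling, under two labels, and one says substance use. The one that differs is the only one that describes how the data are collected.

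**2. Share of the primary outcome.** The primary measures are VAS-craving, TLFB, PG-YBOCS and G-SAS, so the TLFB is 1/4 = 25% of the list. For gambling behaviour they are TLFB, PG-YBOCS and G-SAS, so it is 1/3 = 33%. These are shares of a list of measures, not estimates of lost data.

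**3. Does lifetime recall give a change from baseline?** Let L(0) be a count over the lifetime calendar at baseline, and N(t) the count between baseline and time t. With perfect recall, L(t) = L(0) + N(t). Since N(t) cannot be negative, L(t) is never below L(0). A fall in gambling would not appear as a fall in the lifetime count; it would have to be read from separate parts of the calendar. The entry does not say which parts. By contrast, the PG-YBOCS entry gives a one-week period.

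**4. Do the stated time points supply the windows?** They say when the calendar is completed, not what period is compared. Suppose the three time points are the ends of the three phases, as the schedule for cognitive testing suggests, and each window runs back to the previous time point. The windows are then 2, 12 and 12 weeks. A patient who gambles steadily on one day a week would show 2 × 1 = 2 days, then 12 × 1 = 12 days: a sixfold rise in the raw count with no change in behaviour. Unequal windows therefore need a per-time scale.

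**5. Is the missing content supplied elsewhere?** No section names a TLFB variable such as days gambled or amount wagered. Section E mentions relapse rate and gambling severity. The Aims tie gambling disorder severity to the TLFB, but no section ties relapse rate to any instrument.

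**The case against.** The strongest reply is that the intent is plain. Three outcome statements, in a trial of patients with gambling disorder, say what the TLFB must deliver, so the substance-use phrase is probably a slip. Substance wording also appears in the recruitment paragraph of section C. This stands, and it limits the point to reconciliation. It does not remove it, because staff collect data from the instrument description.

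A second reply is dual use. The entry does not say that the TLFB records only substance use. Nicotine is exempt from the substance-use exclusion, and the separate alcohol criterion bars only moderate to severe disorder, so some substance use can occur in the sample. The toxicology screen is listed only for stimulation days, and the monitoring of illicit drugs mentioned under Side effects names no method. A reader might infer from the drug-free criterion and the screen that dual use is ruled out; the documents do not support that. If dual use is meant, the entry is incomplete and still has to say so.

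Third, the Statistical Analysis paragraph names no summary variable for any instrument, and the G-SAS entry also gives no look-back. That is true. The TLFB differs in that its stated look-back is lifetime, repeated at every visit, and its stated construct is the wrong one for the outcome.

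Fourth, periods before and after treatment could be cut from a calendar. They could, which is why the remedy is wording. No section proposes to analyse lifetime totals, so step 3 above shows what the lifetime look-back cannot deliver by itself, not what the sponsor plans to do.

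**Conclusion.** The contradiction is real and should be fixed. The only description of the TLFB names substance use, while three outcome statements name gambling. Followed as written, the entry produces no gambling data for one of the four primary measures, which is one of the three for gambling behaviour. Correcting the construct alone is not enough, because repeated lifetime recall overlaps baseline and leaves the pre/post comparison undefined.

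A reader might infer that the trial will hold no TLFB gambling data, or that the co-primary goal fails. The documents support neither. The calendar form is not among them, so it may well record gambling. VAS-craving, PG-YBOCS and G-SAS are described separately and are unaffected, and the last two still cover gambling behaviour in this 10-patient, single-arm study.

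The contradiction rests on text alone. The loss of gambling data assumes that the entry is followed literally, and the 2-, 12- and 12-week windows are an assumed illustration.

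**What to change.** Reword the TLFB entry in section D so that it:

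- says the TLFB records gambling behaviour, and uses one label for the construct in the Précis, section D and section F;
- names the variable, for example days gambled or amount wagered, with its unit;
- replaces the repeated lifetime look-back, for the outcome analysis, with stated, comparable, non-overlapping windows for baseline and for 2 weeks, 3 months and 6 months;
- puts values on a common per-time scale, such as days per week, if window lengths differ;
- declares any lifetime history or substance-use recording as a separate, non-primary use.

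The Statistical Analysis paragraph should then refer to the named TLFB variable. The choice of variable, window lengths and model remains with the sponsor and should be fixed before the data are examined.

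The cost is protocol wording and a check that the calendar form captures the chosen variable. No patients or visits are added.
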